Based on an exploratory analysis of response for subjects in the 8-mg daily regimen in Study BLC2001, when a higher phosphate level of 7 mg/dL was used as the new threshold, a larger separation of clinical response was observed between subjects with serum phosphate \geq 7 mg/dL and <7 mg/dL (45.5 vs. 31.6% for ORR; 90.9% vs. 75% for DCR).

Hence, the clinical goal is to maximize the number of subjects reaching the new target phosphate level of 7 mg/dL in order to attain maximum and sustained target inhibition.

Clinical Safety

The 8-mg daily regimen from the ongoing Study BLC2001 was well tolerated and without significant treatment interruptions (approximately 10% to 15% anticipated early interruptions). Up-titration from the 8-mg daily regimen to the 9-mg daily regimen on Cycle 1 Day 14 in subjects with both serum phosphate level below 5.5 mg/dL (ie, suboptimal PD effect) and without significant drug-related toxicity (ie, Grade ≥ 2 toxicity or Grade ≥ 1 central serous retinopathy or retinal pigment epithelial detachments) is likely to have a good overall tolerability profile and increases the likelihood of improved efficacy.

Moreover, the observed safety of the 9-mg daily regimen in the completed Phase 1 Study EDI1001 did not raise concerns about prolonged hyperphosphatemia, and no soft-tissue calcification or electrolyte disturbance or endocrine abnormalities were reported. Similarly, in the ongoing Phase 2 study, no such abnormalities were observed. Therefore, a more aggressive approach to up-titration may be adopted, allowing up-titration in subjects whose Day 14 phosphate is below 7 mg/dL (instead of below 5.5 mg/dL) without concurrent temporary use of phosphate binder treatment, or

whose serum phosphate is between 7 and 9 mg/dL with concurrent temporary use of phosphate binder treatment (see Section 6.1).

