Instructions for up-titration of erdafitinib, in the absence of erdafitinib related toxicity, based on the serum phosphate level at Cycle 1 Day 14 are provided below and in Figure 5. For children aged ≥ 6 to <12 years and adolescents aged ≥ 12 to <15 years, an additional blood sample will be drawn at Cycle 2 Day 7 for determination of the serum phosphate level and the need for dose modification.

Subjects with a serum phosphate level higher than 9.00 mg/dL (>2.91 mmol/L) will withhold erdafitinib treatment, with at least weekly assessment of serum phosphate until it returns to less than 7.00 mg/dL (<2.25 mmol/L) while initiating treatment with a phosphate binder such as sevelamer (see Table 8 for detailed guidelines regarding further treatment).

[figure not shown]

Figure 5: Instructions for up-titration of erdafitinib based on serum phosphate levels

Note: in presence of erdafitinib-related toxicities, the investigator may choose to maintain the same dose of erdafitinib without up-titration.

Adult subjects and adolescent subjects aged ≥ 15 to <18 years

- Adult subjects and adolescent subjects aged ≥15 to <18 years with a serum phosphate level between 7.00 to 8.99 mg/dL (2.25 mmol/L to 2.90 mmol/L) on Cycle 1 Day 14 will increase the erdafitinib dose from 8 mg once daily to 9 mg once daily, while concurrently initiating treatment with a phosphate binder such as sevelamer (see Table 8 for details).
- Adult subjects and adolescent subjects aged ≥15 to <18 years with a serum phosphate level less than 7.00 mg/dL (<2.25 mmol/L) will increase the erdafitinib dose to 9 mg once daily. No concomitant treatment is required for these subjects.

Adolescent subjects aged ≥ 12 to <15 years

- Adolescent subjects aged ≥12 to <15 years with a serum phosphate level between 7.00 to 8.99 mg/dL (2.25 mmol/L to 2.90 mmol/L) will increase the erdafitinib dose from 5 mg once daily to 6 mg once daily on Cycle 1 Day 14 or Cycle 2 Day 7, and further from 6 mg once daily to 8 mg once daily on Cycle 2 Day 7 (for those already up-titrated to 6 mg on Cycle 1 Day 14), while concurrently initiating treatment with a phosphate binder such as sevelamer (see Table 8 for details). This 2-step up-titration is step-wise, ie, no subjects will be allowed to directly up-titrate from 5 mg to 8 mg.

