6.6.1. Guidance for Specific Erdafitinib Toxicities

6.6.1.1. Guidelines for the Management of Elevated Phosphate Levels

Hyperphosphatemia will be graded as outlined in Table 7. Guidelines for the clinical management of elevated serum phosphate levels are presented in Table 8.

For guidance on Cycle 1 up-titration, see Section 6.1.

Adverse Event	Grade 1	Grade 2	Grade 3	Grade 4
Hyperphosphatemia	5.50-6.99 mg/dL 1.75-2.24 mmol/L	7.00-8.99 mg/dL 2.25-2.90 mmol/L	9.00-10.00 mg/dL (2.91-3.20 mmol/L), or asymptomatic soft tissue calcification with any phosphate level	>10.00 mg/dL (>3.20 mmol/L), or symptomatic soft tissue calcification with any phosphate level

 Table 7:
 Grading of Hyperphosphatemia Adverse Events

Serum Phosphate	Innes for Management of Serum Phosphate Ele	
Level	Study Drug Management	Symptom Management
<5.50 mg/dL	Continue erdafitinib treatment.	None.
(<1.75 mmol/L)		
(Grade 0)		
5.50-6.99 mg/dL	Continue erdafitinib treatment.	Restriction of phosphate intake to 600 –
(1.75-2.24		800 mg/day.
mmol/L)		
(Grade 1)	a	
7.00-8.99 mg/dL	Continue erdafitinib treatment.	Restriction of phosphate intake to 600 –
(2.25-2.90		800 mg/day.
mmol/L)	A dose reduction will be implemented for	
(Grade 2)	persistent ^a hyperphosphatemia (defined as serum phosphate ≥7.00 mg/dL for a period of 2 months) or if clinically necessary (eg, in the presence of additional adverse events linked	Adults: Start sevelamer 800 to 1,600 mg TID with food until phosphate level is <7.00 mg/dL.
	to hyperphosphatemia or electrolyte disturbances)	Children and adolescents: Start sevelamer 400 mg TID for BSA 0.75 m ² , 800 mg
		TID for BSA ≥ 0.75 to $<1.2 \text{ m}^2$, and 1,600 mg for BSA $\geq 1.2 \text{ m}^2$ with food. Titrate up/down by 200 mg for BSA 0.75 m ² , 400 mg TID for BSA ≥ 0.75 to $<1.2 \text{ m}^2$, and 800 mg for BSA $\geq 1.2 \text{ m}^2$ until phosphate level is $<7.00 \text{ mg/dL}$. ^b
9.00-10.00 mg/dL (2.91-	Withhold ^c erdafitinib treatment until serum phosphate level returns to 7.00 mg/dL (weekly	Restriction of phosphate intake to 600 – 800 mg/day.
3.20 mmol/L)	testing recommended).	
(Grade 3)	Re-start treatment at the same dose level.	Adults: Sevelamer up to 1,600 mg TID with food until serum phosphate level
	A deservation will be implemented for	returns to $<7.00 \text{ mg/dL}$.

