	A dose reduction will be implemented for persistent ^a hyperphosphatemia (defined as serum phosphate ≥9.00 mg/dL for a period of 1 month) or if clinically necessary (eg, in the presence of additional adverse events linked to hyperphosphatemia or electrolyte disturbances)	Children and adolescents: Start sevelamer 400 mg TID for BSA 0.75 m ² , 800 mg TID for BSA \geq 0.75 to <1.2 m ² , and 1,600 mg for BSA \geq 1.2 m ² with food. Titrate up/down by 200 mg for BSA 0.75 m ² , 400 mg TID for BSA \geq 0.75 to <1.2 m ² , and 800 mg for BSA \geq 1.2 m ² until phosphate level is <7.00 mg/dL. ^b
>10.00 mg/dL (>3.20 mmol/L) (Grade 4)	Withhold ^c erdafitinib treatment until serum phosphate level returns to 7.00 mg/dL (weekly testing recommended).	Medical management as clinically appropriate.
	Re-start treatment at the first reduced dose level.	
	If persistent ^a hyperphosphatemia $(\geq 10.00 \text{ mg/dL})$ for >2 weeks, erdafitinib should be discontinued permanently.	
Significant	Erdafitinib should be discontinued	Medical management as clinically
alteration in baseline renal	permanently. (In situations where the subject is having clinical benefit and the investigator and the sponsor's medical monitor agree that	appropriate.

 Table 8:
 Guidelines for Management of Serum Phosphate Elevation

Serum Phosphate		
Level	Study Drug Management	Symptom Management
function or Grade 3	continuation of treatment is in the best interest	
hypocalcemia	of the subject, the drug may be re-started at	
	2 dose levels lower if appropriate. Follow	
	other recommendations described above,	
	Section 6.6.)	

 Table 8:
 Guidelines for Management of Serum Phosphate Elevation

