Note: These are general guidelines that are based on emerging data and consensus experience of participating investigators or the experts in the field. The treating physicians must use clinical judgment and local standard of care to decide the best way to manage phosphate elevation. If sevelamer hydrochloride (Renagel[®]) is not available, use of other phosphate binders (non-calcium containing) based on the local standard is recommended, including sevelamer carbonate (Renvela) or lanthanum carbonate (Fosrenol[®]). These guidelines will be updated based on emerging data. Additional information on phosphorous in foods by class of food can also be found at www.permanente.net/homepage/kaiser/pdf/42025.pdf. Additional information for phosphate management and diet can be found at the National Kidney Foundation website (http://www.kidney.org/atoz/content/phosphorus.cfm).

a. Persistent hyperphosphatemia is considered to be more than 1 sequential phosphate value above the cut-off.

b. Pediatric dosing for sevelamer based on Fathallah-Shaykh 2018.

c. Study drug interruptions for hyperphosphatemia suggested to be 7 days in duration.

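### Protocol Table 8 defines persistent hyperphosphatemia by duration in the Grade 2 and Grade 3 cells and by a count of values in footnote a, and does not say how the two combine

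*Protocol*

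**What the plan says.** Table 8 in Protocol Section 6.6.1.1 attaches marker a to the word *persistent* in the Grade 2, Grade 3 and Grade 4 rows.

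- Grade 2: a dose reduction is required for persistent "hyperphosphatemia (defined as serum phosphate ≥7.00 mg/dL for a period of 2 months".
- Grade 3: a dose reduction is required for persistent "hyperphosphatemia (defined as serum phosphate ≥9.00 mg/dL for a period of 1 month".
- Grade 4: if persistent hyperphosphatemia at 10.00 mg/dL or more lasts "for >2 weeks, erdafitinib should be discontinued permanently".
- Footnote a: "Persistent hyperphosphatemia is considered to be more than 1 sequential phosphate value above the cut-off".

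Both the Grade 2 and the Grade 3 cell also allow a reduction on clinical need. The note under the table describes its content as general guidance that leaves room for clinical judgment and local practice.

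Two other sections bear on the point. Section 4.3 states that "the clinical goal is to maximize the number of subjects reaching the new target phosphate level of 7 mg/dL". Section 6.1 raises the dose, in the absence of erdafitinib-related toxicity, when phosphate is 7.00 to 8.99 mg/dL, together with a phosphate binder. For adults and adolescents aged 15 to under 18 years this is one step at Cycle 1 Day 14. For subjects aged 6 to under 15 years it can happen at Cycle 1 Day 14 and again at Cycle 2 Day 7.

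**The concern.** The same word has two definitions of different kinds. The cells ask how long phosphate has been high; the footnote asks how many values in a row were high. A site that follows the footnote could reduce the dose at the second high value. A site that follows the Grade 2 cell would wait 2 months. Because the reduction is worded as mandatory, the choice of reading decides what happens to the subject.

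The Grade 2 range is also the range the dose rationale aims for, so the rule concerns subjects in whom the regimen is doing what it was designed to do. SAP Section 4.4 summarizes dose adjustments and their reasons, and the table in SAP Section 6.1.1 lists events leading to dose modification. Different readings by site would therefore enter the reported exposure and tolerability results.

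**Working it through.** The plan gives no figure of its own to reproduce. The check compares the shortest time in which the scheduled tests can satisfy the footnote with the duration in each cell.

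**Inputs**
- Cycle length: 21 days (Synopsis and Section 6.1).
- Adult chemistry, which includes phosphate: Day 1 and Day 14 in Cycles 1 to 3, Day 1 only from Cycle 4 (Section 1.3; Section 10.2).
- Children and adolescents: an additional chemistry draw at Cycle 2 Day 7 (Section 1.4). Section 6.1 uses it for titration at ages 6 to under 15 years.
- While drug is withheld for high phosphate, Section 6.1 requires testing "with at least weekly assessment of serum phosphate until it returns to less than 7.00 mg/dL".
- Month length: taken as 30.4 days (assumption), so 2 months is 2 × 30.4 = 60.8 days.

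**Gap between consecutive scheduled values**, where study day = (cycle − 1) × 21 + cycle day
- Cycle 1 Day 14 to Cycle 2 Day 1: 22 − 14 = 8 days. With the visit windows alone (+2 on Day 14, ±2 on Day 1) it runs from 20 − 16 = 4 to 24 − 14 = 10 days.
- Day 1 to Day 14 of the same cycle: 13 days.
- Cycle 2 Day 1 to Day 7, and Day 7 to Day 14 (children and adolescents): 6 and 7 days.
- From Cycle 4, Day 1 to Day 1: 21 days.

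**Footnote against cell**

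| Rule | Footnote met after | Cell duration | Ratio |
|---|---|---|---|
| Grade 2, adults, Cycles 1 to 3 | 8 days | 60.8 days | 60.8 / 8 = 7.6 |
| Grade 2, adults, Cycle 4 onward | 21 days | 60.8 days | 60.8 / 21 = 2.9 |
| Grade 3, weekly testing | 7 days | 30.4 days | 30.4 / 7 = 4.3 |

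The 8-day case is the widest for adults and applies only to Grade 2 in the first three cycles. At Grade 3 the drug is already withheld at the first such value, so persistence bears on the dose at restart and not on the interruption.

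**Footnote against Section 6.1**

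Take a subject aged 6 to under 15 years, without erdafitinib-related toxicity, whose phosphate is 7.00 to 8.99 mg/dL at Cycle 1 Day 14, Cycle 2 Day 1 and Cycle 2 Day 7. Section 6.1 raises the dose at Cycle 1 Day 14 and again at Cycle 2 Day 7, which is 28 − 14 = 14 days later. Footnote a, read alone, is met at Cycle 2 Day 1, after 8 days, and Table 8 then calls for a reduction. The 2-month cell is not met at any of these visits. If the Cycle 2 Day 1 value is below 7.00, the high values are not sequential and the conflict does not arise at Day 7. Section 6.6.1.1 refers the reader to Section 6.1 only for up-titration in Cycle 1, so it does not settle Cycle 2 Day 7.

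**The case against.** The best answer is that the footnote sets a minimum of evidence: at least two high values, in addition to the duration in the cell. The footnote names no threshold of its own, so its cut-off has meaning only through the cell, and the cells carry the explicit, grade-specific definitions. The titration text in Section 6.1 is also hard to square with a footnote that triggers a reduction by itself. This reading is plausible and would remove the conflict. The protocol does not state it, however. It also leaves the footnote little to do, since 2 months of 21-day cycles or 1 month of weekly tests would ordinarily yield at least two values anyway.

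The table's status as guidance subject to clinical judgment also stands. Some variation between sites is built in whichever definition applies, and this limits the practical effect. It does not tell a site which definition to start from.

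Two stronger readings are tempting, and the documents support neither.

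- A reader might infer that permanent discontinuation at Grade 4 also turns on the footnote, because that row carries the same marker. In the Grade 4 sentence the period of more than 2 weeks is a condition separate from the word *persistent*. Putting the footnote's meaning in place of that word leaves the 2 weeks intact.
- A reader might add the two adult figures in Section 4.3, 21.6% within the target range and 6.9% above 9 mg/dL, to get 28.5% of adults affected. These are simulated proportions at week 6 only. They do not measure persistence or disagreement between the definitions. They do not bound it either: subjects with two high values at other times are not counted, and subjects with a single high value are.

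**Conclusion.** The point holds for the Grade 2 and Grade 3 dose-reduction rules. It is an ambiguity with operational consequences, and it does not show that either definition is the wrong one. On scheduled adult tests the two readings differ by 8 days against about 61 in Cycles 1 to 3 and by 21 days against about 61 from Cycle 4 at Grade 2. At Grade 3 they differ by about 7 days against about 30. These figures assume on-schedule visits, weekly testing while drug is withheld, no unscheduled draws and a 30.4-day month. For ages 6 to under 15 years the footnote read alone can call for a reduction in a subject whom Section 6.1 up-titrates, provided the intervening Cycle 2 Day 1 value is also high.

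The documents do not allow an estimate of how many subjects would be managed differently. The effect is on dose-modification and tolerability data. The response-rate definition, alpha, power and sample size are not touched.

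**What to change.** Reconcile footnote a of Table 8 with the Grade 2 and Grade 3 cells and with the up-titration text in Section 6.1, so that one definition applies per grade and the text says whether the count of values replaces the duration or adds to it. Since the marker also sits on the Grade 4 row, state there too how the footnote and the period of more than 2 weeks relate. Which rule should apply is for the sponsor; no view is offered here.

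The cost is wording only. Under Section 10.3.1 a protocol clarification communication is enough if study conduct does not change; otherwise a protocol amendment is needed. No new data collection is required.

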6.6.1.2. Guidelines for the Management of Dry Mouth and Mucositis

Guidelines for the clinical management of dry mouth (xerostomia) and mucositis are provided in Table 9 and Table 10, respectively.

General prophylaxis for dry mouth and oral mucositis:

- Good oral hygiene
- Use a soft toothbrush
- Avoidance of spicy, acidic, hard, and hot food and beverages
- Use of mild-flavored toothpastes
- Use of salt and baking soda mouthwashes 3 or 4 times per day
- Water soluble lubrication agents like artificial saliva (for xerostomia or dry mouth)

Grade and Definition	Study Drug (Erdafitinib) Management	Symptom Management
Grade 1: symptomatic (eg, dry or thick saliva) without significant dietary alteration; unstimulated saliva flow >0.2 mL/min	Continue erdafitinib at current dose.	Sorbitol lozenges as needed
Grade 2: moderate symptoms; oral intake alterations (eg, copious water, other lubricants, diet limited to purees or soft, moist foods); unstimulated saliva 0.1 to 0.2 mL/min	Continue erdafitinib at current dose.	Sorbitol lozenges as needed and Cevimeline 30 mg TID or Pilocarpine 5 mg TID, orally
Grade 3: inability to adequately aliment orally; tube feeding or TPN indicated; unstimulated saliva less than 0.1 mL/min	Hold erdafitinib (for up to 28 days), with weekly reassessments of clinical condition. When resolved to \leq Grade 1 or baseline, restart at 1 dose level below in consultation with the medical monitor.	Sorbitol lozenges as needed and Cevimeline 30 mg TID or Pilocarpine 5 mg TID, orally
Grade 4: life-threatening consequences, urgent intervention indicated	Discontinue erdafitinib.	Evaluation and therapy as clinically indicated

 Table 9:
 Guidelines for Management of Dry Mouth (Xerostomia)

Table 10:	Guidelines for	r the Management	of Oral Mucositis
1 4010 101	Guidennes io	i the management	or or ar macositis

Grade	Study Drug (Erdafitinib) Management	Symptom Management
Grade 1	Continue erdafitinib at current dose.	 Continue general prophylaxis recommendations Dexamethasone solution (0.5 mg/5mL solution) swish and spit QID or similar solution that is available in your country/territory and lidocaine 2-5% jelly or solution. Consider clotrimazole/nystatin if subjects are at risk of developing oral candidiasis.
Grade 2	 Consider holding erdafitinib if the subject has other study-drug related concomitant Grade 2 AEs. Hold erdafitinib if the subject was already on symptom management (dexamethasone solution swish and spit and lidocaine 2%-5% jelly or solution) for more than a week. If the erdafitinib is withheld, reassess in 1-2 weeks. If this is the first occurrence of toxicity and resolves to ≤Grade 1 or baseline within 2 weeks, restart at same dose. If recurrent event or takes >2 weeks to resolve to ≤Grade 1 or baseline, then restart at 1 dose level below. 	 Dexamethasone solution (0.5 mg/5mL solution) swish and spit QID or similar solution that is available in your country/territory and lidocaine 2-5% jelly or solution. Consider concomitant etiologies such as oral candidiasis, oral herpes and recommend appropriate anti-fungal or anti-viral agents.

Grade	Study Drug (Erdafitinib) Management	Symptom Management
Grade 3	 Hold erdafitinib, with reassessments of clinical condition in 1-2 weeks. When resolves to ≤Grade 1 or baseline, restart at 1 dose level below in consultation with the medical monitor. 	 Dexamethasone solution (0.5 mg/5mL solution) swish and spit QID or similar solution that is available in your country/territory and lidocaine 2%-5% jelly or solution. Consider pain management strategies. Consider IV hydration.
Grade 4	Discontinue erdafitinib.	Evaluation and therapy as clinically indicated.

 Table 10: Guidelines for the Management of Oral Mucositis

6.6.1.3. Guidelines for the Management of Dry Skin and Skin Toxicity

Guidelines for the management of dry skin are provided in Table 11.

General prophylaxis for dry skin and skin toxicity:

- Avoid unnecessary exposure to sunlight and excessive use of soap.
- Avoid bathing in excess; use tepid rather than hot water.
- Use moisturizers regularly; apply thick, alcohol-free and oil-in-water based emollient cream on exposed and dry areas of the body.
- Avoid perfumed products, bubble bath, perfumed soaps, and take breaks from shaving.
- Use broad spectrum sunscreen with a skin protection factor (SPF) ≥ 15 .
- Wear cotton clothes next to skin rather than wool, synthetic fibers, or rough clothing.
- Use occlusive alcohol-free emollient creams (jar or tub) for treatment of mild/moderate xerosis.
- For scaly areas, use exfoliants (ammonium lactate 12% or lactic acid cream 12%).

Grade and Definition	Study Drug (Erdafitinib) Management	Symptom Management
Grade 1: Dry skin covering less than 10% body surface area (BSA) and no associated erythema or pruritus	Continue erdafitinib at current dose.	Use fragrance free moisturizing cream or ointment BID over entire body. Use ammonium lactate 12% cream or salicylic acid 6% cream BID over dry/scaly/hyperkeratotic areas such as palms and soles.
Grade 2: Dry skin covering 10% to 30% BSA and associated with erythema or pruritis with limited instrumental activities of daily living (IADL)	Continue erdafitinib at current dose.	Use fragrance free moisturizing cream or ointment BID over entire body. Use ammonium lactate 12% cream or salicylic acid 6% cream BID over dry/scaly/hyperkeratotic areas such as palms and soles. Use zinc oxide 13%-40% at night for areas with fissures.
Grade 3: Dry skin covering >30% BSA and associated with pruritis; limiting self-care activities of daily living (ADL)	Hold erdafitinib (for up to 28 days), with weekly reassessments of clinical condition. When resolves to ≤Grade 1 or baseline, restart at 1 dose level below in consultation with the medical monitor.	Use topical steroid ointment or cream* BID and zinc oxide 13%- 40% at night for areas with fissures.
Grade 4: Dry skin with life- threatening consequences, urgent intervention indicated	Discontinue erdafitinib. obetasol 0.05%, Betamethasone 0.05%, Fluc	Evaluation and therapy as clinically indicated

 Table 11:
 Guidelines for Management of Dry Skin

6.6.1.4. Guidelines for the Management of Nail Toxicity (Onycholysis, Onychodystrophy, and Paronychia)

Adverse events related to nails will be graded as outlined in Table 12. Guidelines for the management of nail discoloration/loss/ridging (onycholysis/onychodystrophy) nail toxicity are provided in Table 13. Guidelines for the management of paronychia are provided in Table 14.

Adverse Event	Grade 1	Grade 2	Grade 3	Grade 4
Nail Changes	Nail discoloration,	Nail/finger tips	Severe nail finger	Life-threatening
(onychodystrophy)	asymptomatic	pain, symptomatic	tips pain,	consequences,
	separation of the	separation of the	symptomatic	urgent intervention
	nail bed from the	nail bed from the	separation of the	indicated
	nail plate or nail	nail plate or nail	nail bed from the	
	loss	loss; limiting	nail plate or nail	
		instrumental ADL	loss; significantly	
			limiting	
			instrumental ADL	

 Table 12:
 Grading of Nail Adverse Events

ADL= activities of daily living

General prophylaxis for nail toxicity:

- Good hygienic practices, keep fingers and toes clean
- Keep nails trimmed but avoid aggressive manicuring
- Use gloves for housecleaning and gardening to minimize damage and prevent infection
- Nail polish and imitation fingernails should not be worn until the nails have grown out and returned to normal
- Wearing comfortable shoes (wide sized shoes with room for the toes)

the set of	 Continue general prophylaxis recommendations Over the counter nail strengthener OR polyurea-urea urethane nail lacquer (Nuvail™) OR diethylene glyco monoethylether nail lacquer (Genadur) daily. Use non- alcohol-containing moisturizing creams. Manage as per Grade 1 For signs of infection (periungual edema/erythema/ tenderness or discharge), obtain bacterial cultures, and then start the following: treatment with oral antibiotic for 2 weeks (cefadroxil 500 mg BID, ciprofloxacin 500 mg BID, or sulfamethoxazole/ trimethoprim BID)
ecurrent event or takes >2 weeks to	 For signs of infection (periungual edema/erythema/ tenderness or discharge), obtain bacterial cultures, and then start the following: treatment with oral antibiotic for 2 weeks (cefadroxil 500 mg BID, ciprofloxacin 500 mg BID, or sulfamethoxazole/ trimethoprim
art at 1 dose level below in sultation with the medical monitor.	AND • topical antifungal lacquer daily for 6+ weeks (ciclopirox olamine 8% OR efinaconazole 10% OR amorolfine 5% weekly OR bifonazole/urea ointment daily) • Silver nitrate application weekly AND topical antibiotics AND vinegar soaks ^a
d erdafitinib, with reassessment in weeks. en resolves to ≤Grade 1 or baseline, art at 1 dose level below in sultation with the medical monitor.	Silver nitrate application weekly AND topical antibiotics AND vinegar soaks. ^a For signs of infection (periungual edema/erythema/ tenderness or discharge), obtain bacterial cultures, and then start the following: treatment with oral antibiotic for 2 weeks (cefadroxil 500 mg BID, ciprofloxacin 500 mg BID, or sulfamethoxazole/trimethoprim BID). For cases of severe/refractory infection consider intravenous antibiotics. Consider dermatological or surgical evaluation.
continue erdafitinib.	Evaluation and therapy as clinically indicated.
	1 erdafitinib, with reassessment in weeks. en resolves to ≤Grade 1 or baseline, art at 1 dose level below in sultation with the medical monitor.

Table 13:	Guidelines for Management of Nail Toxicity (Onycholysis/ Onychodystrophy)
1	Guldennes for Mundgement of Munder (Ongenergists, Ongenergists)

Grade	Study Drug (Erdafitinib) Management	Symptom Management
Grade 1	Continue erdafitinib at current dose.	Topical antibiotics AND vinegar soaks ^a
Grade 2	Continue erdafitinib at current dose. Consider erdafitinib holding if no improvement in 1 to 2 weeks. When resolves to ≤Grade 1 or baseline, restart at same or 1 dose level below in consultation with the medical monitor	Topical antibiotics AND vinegar soaks ^a AND topical antifungal lacquer daily for 6+ weeks (ciclopirox olamine 8% OR efinaconazole 10% OR amorolfine 5% weekly OR bifonazole/urea ointment daily) For signs of infection (periungual edema/erythema/tenderness or discharge), obtain bacterial cultures, and then start the following: treatment with oral antibiotic for 2 weeks (cefadroxil 500 mg BID, ciprofloxacin 500 mg BID, or sulfamethoxazole/ trimethoprim [Bactrim TM DS BID).
Grade 3	Hold erdafitinib (for up to 28 days), with weekly reassessments of clinical condition. When resolves to ≤Grade 1 or base line, restart at one dose level below in consultation with the medical monitor.	Vinegar soaks ^a AND consider nail avulsion For signs of infection (periungual edema/erythema/tenderness or discharge), obtain bacterial cultures, and then start the following: treatment with oral antibiotic for 2 weeks (cefadroxil 500 mg BID, ciprofloxacin 500 mg BID, or sulfamethoxazole/ trimethoprim [Bactrim DS BID). For cases of severe/refractory infection consider intravenous antibiotics. Consider dermatological or surgical evaluation.

Table 14: **Guidelines for Management of Paronychia**

day. Examples of topical antibiotic ointments: Mupirocin 2%, gentamycin, bacitracin zinc/polymixin B

